## Statistical Methods

**Number of subjects planned to be enrolled:** About 80 providers will enrolled.

## Justification of Sample Size

The sample size of 80 is based on feasibility: on an assumption that about 50% of providers in the selected facilities are likely to participate in the intervention. This sample size is powered (at 80%) to detect an effect size of about 0.5. The length of the pilot study might, however, be too short to see such an effect size. Thus, the pilot is likely not powered for formal significance testing. The effect size estimates from the pilot will be used to inform the sample size estimation for the R01 trial.

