### (d) Sampling

#### (i) Sample size determination

For the qualitative formative research, a sample size of 20 is estimated to achieve saturation. For the evaluation, we expect to enroll 80 providers, with 40 in the intervention group and 40 in control group. This is a pilot study and the sample size of 80 is based on feasibility: on an assumption that about 50% of providers in the selected sub-counties are likely to participate in the intervention. This sample size is powered (at 80%) to detect an effect size of about 0.5. The results will be used to determine the sample size for the R01 clinical trial

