#### (ii) Sampling procedure

About 20 people, including providers and county leadership, will be recruited for the formative research which will use in-depth interviews and 80 providers for the evaluation, which will use both structured and in-depth interviews. 40 providers will be assigned to the intervention group and another 40 in the control group. Assignment will be at the facility level, based on which facilities are selected as the intervention and control facilities. Thus, all providers in the two intervention facilities will be assigned to the intervention group. Providers from other facilities will be assigned to the control group. All 80 providers will be asked to participate in the baseline and end line surveys. We will collect contact information at baseline to follow up for the end line survey for the evaluation data. Providers will be purposively selected based on their position in the facility and involvement in maternity care. Providers will include both male and female clinical and support staff such as ward aids and community health workers who assist in various roles on the ward. We will assess the feasibility and acceptability of including the support staff in the formative phase.

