### **(c) Data management and analysis plan**

**Aims 2&3:** We will record all in-depth interviews and transcribe them verbatim. We will use the REDCap application to conduct the quantitative surveys. The data collected with this application is uploaded directly to a secure online server and immediately available for analysis. This will enable us to do data quality checks while the data is being collected to address any issues in a timely manner. We will ensure confidentiality of all participants in the data collection and storage.

We will use thematic analysis to analyze the qualitative data on feasibility and acceptability. We will use Braun and Clark's approach to thematic analysis. This is an iterative process getting familiar with the data, generating initial codes, searching for themes, reviewing themes, defining and naming themes, and producing the report. We will use the Dedoose software for coding the data.

For the quantitative data, the merged dataset will be imported into Stata for analysis. We will examine the univariate and bivariate distributions of all variables and conduct appropriate multivariate analysis: logistic regressions for categorical outcomes and linear regression for continuous outcomes. We will use a difference in differences approach to assess intervention effects: for a given outcome, the intervention effect is the outcome change from baseline to end line for the intervention group ( $T2i - T1i$ ) minus that for the control group ( $T2c - T1c$ ). Where applicable, we will use mediation and moderation analyses to examine intervening and conditional effects. We will use intent to treat design, which is recommended for understanding intervention effectiveness.

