### Analysis of primary outcomes at baseline and endline for control and intervention groups

We will generate descriptive statistics (both mean with standard deviation, and median with the range) to understand the distribution of each of the outcome variable at both baseline and end line for control or intervention groups. We will use a Wilcoxon paired signed-rank test to determine whether changes in the outcome measures are different between baseline and endline for control or intervention group. These results will be presented in a Table 3.

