**Table 3: Estimates of primary outcomes at baseline and endline**

Outcome measure	Statistic	Overall estimates		P
		Baseline	End line	
Control Group (N=40)				
Intervention Group (N=40)				

We will then use a difference in differences approach to assess intervention effects: For a given outcome, the intervention effect is the outcome change from baseline to end line for the intervention group ( $T2i - T1i$ ) minus that for the control group ( $T2c - T1c$ ).

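### The 80% power stated for an effect of about 0.5 is not reproduced for the between-group effect under usual assumptions; at an assumed two-sided 5% level and baseline–endline correlation of 0.5 it is about 60%

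*Combined protocol and SAP*

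**What the plan says.** The protocol, under (d)(i) Sample size determination, gives feasibility as the basis for the number: "This is a pilot study and the sample size of 80 is based on feasibility". It then makes a power claim, which the SAP repeats under Justification of Sample Size: "This sample size is powered (at 80%) to detect an effect size of about 0.5". Allocation is 40 intervention and 40 control.

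The SAP adds two sentences that the protocol lacks: "The length of the pilot study might, however, be too short to see such an effect size" and "Thus, the pilot is likely not powered for formal significance testing".

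On analysis, the SAP names one test for the outcomes, applied within each arm: "We will use a Wilcoxon paired signed-rank test to determine whether changes in the outcome measures are different between baseline and endline". The intervention effect is a separate, between-group quantity: "We will then use a difference in differences approach to assess intervention effects". The protocol's analysis plan defines it in the same way: "the intervention effect is the outcome change from baseline to end line for the intervention group", less the corresponding change in controls. On allocation, the protocol says: "Assignment will be at the facility level, based on which facilities are selected as the intervention and control facilities".

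Neither document gives a significance level, sidedness, effect-size scale, baseline–endline correlation, intracluster correlation or expected loss.

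**The concern.** A reader will take the power sentence to describe the comparison that matters, intervention against control. On that reading, a true effect of 0.5 would be missed one time in five. Under the usual two-sided 5% level, a simple comparison of 40 with 40 misses it about two times in five.

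The SAP's caveat does not correct this. It says the pilot may be too short for an effect of that size to appear. That leaves standing the claim that such an effect, if present, would be detected 80% of the time. In the protocol the claim has no power caveat at all.

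At stake are the reading of a null between-group result and the apparent precision of estimates that will inform the size of the later trial.

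**Working it through.** **Inputs from the documents:** 40 per group; effect size about 0.5; power 80%; difference in differences between groups; paired signed-rank test within each arm.

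**Assumptions (not in the documents):** two-sided 5%; effect expressed in baseline SDs, with equal SD at both times; baseline–endline correlation r of 0.3, 0.5 or 0.7; all 80 analysed; no clustering. Power is from the noncentral t distribution.

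**1. Attempt to reproduce the 80%: two groups, endline values only.** The noncentrality is 0.5 × √(40/2) = 2.236 on 78 degrees of freedom.
- Two-sided 5%: power 59.8%.
- One-sided 5%: power 71.6%.
- One-sided 10%: power 82.7%, but nothing in the documents points to that level.
- Effect detectable with 80% power, two-sided 5%: 0.634 SD.
- Number needed for 80% power at 0.5 SD: 64 per group (63 gives 79.5%).

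The same figures apply to change scores if 0.5 is read as SDs of change.

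**2. The planned difference in differences, effect in baseline SDs.** The SD of a change is √(2(1−r)), so the effective standardised difference is 0.5/√(2(1−r)). The detectable effect at 80% power is 0.634 × √(2(1−r)). The 95% CI half-width is t(0.975, 78) × √(2/40) × √(2(1−r)) = 0.445 × √(2(1−r)).

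| Assumed r | √(2(1−r)) | Power for 0.5 SD | Detectable at 80% | CI half-width |
|---|---|---|---|---|
| 0.3 | 1.183 | 46.3% | 0.75 SD | ±0.53 SD |
| 0.5 | 1.000 | 59.8% | 0.63 SD | ±0.45 SD |
| 0.7 | 0.775 | 81.4% | 0.49 SD | ±0.34 SD |

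Power of exactly 80% at 0.5 SD requires 2(1−r) = (0.5/0.634)² = 0.62, so r is about 0.69.

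**3. The within-arm paired test, n = 40.** For 0.5 SD of change the noncentrality is 0.5 × √40 = 3.162. Power is 86.9% by paired t, and about 86% by simulation of the signed-rank test with normal changes. The change detectable with 80% power is 0.45 SD by paired t. Rounded, that is about 0.5, so this calculation roughly fits the stated sentence. It asks whether one arm changed from baseline, not whether the two arms changed differently.

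**4. What is left out.** Loss lowers power: with an assumed 10% or 20% loss, 60% falls to about 55% or 50%. Facility-level assignment needs more care. A facility effect that is constant over time cancels from a change score; only facility differences in change over time would reduce power. The documents give no figure for either.

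**The case against.** The strongest reply is that the figure is under-specified, not wrong. The plan says about 0.5, so the rounded quantity is the detectable effect. The only outcome test the SAP names then gives 80% power at 0.45 SD of change. The difference in differences also reaches 80% if the correlation is near 0.69. Regression on baseline, which neither document specifies, would need about 0.62. This stands. A reader might infer that the 80% is an arithmetical error or that no calculation could produce it; with the inputs unstated, the documents do not support that. What they support is narrower: the figure is not reproduced for the between-group effect at a usual level without a fairly high correlation that is stated nowhere.

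A second reply is that the SAP already concedes the pilot is probably underpowered, bases its size on feasibility and calls the aim preliminary. That limits the consequence, and no decision rule depends on the 80%. It does not cure the sentence, because the stated reason is duration and the 80% is left in place.

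Two further stronger readings should be resisted. One is that the trial needs 64 per group: the number was set by feasibility, so the calculation creates no case for more enrolment. The other is that facility-level assignment must lower every figure above: for change scores, the most that can be said is that it may.

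**Conclusion.** The point holds as one of reporting, and should be fixed. For the between-group effect that the plan estimates, 40 per group is not shown to give 80% power for 0.5. At an assumed two-sided 5% level the difference in differences has about 60% power for 0.5 baseline SD if the correlation is 0.5, and 46% to 81% over correlations of 0.3 to 0.7. The expected CI half-width at a correlation of 0.5 is about ±0.45 SD, nearly as large as the effect named. These figures rest on the assumed level, scale and correlations, and on full follow-up without facility-level variation in change. The sample size and its feasibility rationale are unaffected.

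**What to change.** In both sample size sections, keep the feasibility rationale and replace the power sentence with:

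> With 40 per group and assuming a two-sided 5% level, the difference in differences has about 60% power for 0.5 baseline SD and 80% power for about 0.63 SD at an assumed baseline–endline correlation of 0.5 (46% to 81% power for 0.5 SD at correlations of 0.3 to 0.7), with a 95% CI half-width of about ±0.45 SD; loss to follow-up would lower these figures, and facility-level differences in change over time may lower them.

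If the sponsor has the inputs behind the 80%, it may instead keep that figure, stating the test, significance level, effect-size scale and correlation, and saying so if it refers to the within-arm test.

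Carry the SAP's conclusion, "Thus, the pilot is likely not powered for formal significance testing", into the protocol section.

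The cost is wording in two places, with no added enrolment, data collection or analysis. The stated power becomes less favourable unless the inputs behind the 80% are supplied.

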## Description of the study

### Characteristics of study facilities

We will provide a summary table showing the capacity of each maternity unit in terms of beds, number of deliveries per year, and number of providers for in different cadres: doctors, clinical officers, nurses/midwives, and other staff.

Table 1: Characteristics of Study facilities

Facility	Maternity Bed capacity	Deliveries Per year	Number Providers in Maternity Unit			
			Doctors	Clinical Officers	Nurses/ midwives	Support staff

### Baseline characteristic of the study participants

We will provide a summary of participants characteristics by study group. The summary will be presented in Table 2

Table 2: Baseline characteristic of the study participants

Characteristics	Category	Control (N=40)	Intervention (N=40)	P value
		Frequency (%)	Frequency (%)	

--	--	--	--	--

### Analysis of primary outcomes at baseline and endline for control and intervention groups

We will generate descriptive statistics (both mean with standard deviation, and median with the range) to understand the distribution of each of the outcome variable at both baseline and end line for control or intervention groups. We will use a Wilcoxon paired signed-rank test to determine whether changes in the outcome measures are different between baseline and endline for control or intervention group. These results will be presented in a Table 3.

**Table 3: Estimates of primary outcomes at baseline and endline**

Outcome measure	Statistic	Overall estimates		P
		Baseline	End line	
Control Group (N=40)				
Intervention Group (N=40)				

We will then use a difference in differences approach to assess intervention effects: For a given outcome, the intervention effect is the outcome change from baseline to end line for the intervention group ( $T2i - T1i$ ) minus that for the control group ( $T2c - T1c$ ).

### Analysis of secondary outcomes at baseline and endline for control and intervention groups

We will adopt a similar analysis plan like for the primary outcomes in sections **5.3 and 5.4**. Briefly, we will generate descriptive statistics to understand the distribution of these outcomes at both baseline and end line for control and intervention groups, and we will use a Wilcoxon paired signed-rank test to determine whether changes in the outcome measures are different between baseline and endline for the control or intervention groups. We will finally use a difference in differences approach to assess intervention effects.

1            **References**

2            1. Broman-Fulks J, Kelso K. Stress Management. In: *Wellness Literacy*. 2nd ed. Kendall/Hunt Publishing Co ,U.S.; 2012.

3            2. Surinder S, Meyer C. quiz: test your knowledge oF unconscious bias. Published online 2018. <https://fsae.memberclicks.net/assets/DEI/Quiz-Unconcsious%20Bias.pdf>

4            3. Cohen S, Kamarck T, Mermelstein R. A global measure of perceived stress. *J Health Soc Behav*. 1983;24(4):385-396.

5            4. Afulani PA, Ongeri L, Kinyua J, Temmerman M, Mendes WB, Weiss SJ. Psychological and physiological stress and burnout among maternity providers in a rural county in Kenya: individual and situational predictors. *BMC Public Health*. 2021;21(1):453. doi:10.1186/s12889-021-10453-0

6            5. Nutor JJ, Aborigo RA, Okiring J, et al. Individual and situational predictors of psychological and physiological stress and burnout among maternity providers in Northern Ghana. *PLOS ONE*. 2022;17(12):e0278457. doi:10.1371/journal.pone.0278457

7            6. Afulani PA, Nutor JJ, Agbadi P, et al. Job satisfaction among healthcare workers in Ghana and Kenya during the COVID-19 pandemic: Role of perceived preparedness, stress, and burnout. *PLOS Global Public Health*. 2021;1(10):e0000022. doi:10.1371/journal.pgph.0000022

8            7. Manzar MD, Salahuddin M, Peter S, et al. Psychometric properties of the perceived stress scale in Ethiopian university students. *BMC Public Health*. 2019;19(1):41. doi:10.1186/s12889-018-6310-z

9            8. Shirom A, Melamed S. A comparison of the construct validity of two burnout measures in two groups of professionals. *International Journal of Stress Management*. 2006;13(2):176-200. doi:10.1037/1072-5245.13.2.176

